#### 7.2.2 ANET Procedure

The ANET Applicator and RF generator will be prepared for use per the ANET Instructions for Use (IFU). ASA guidelines for the Prevention and Management of Operating Room fires will be followed, including:

- Discuss the use of RF prior to the procedure with the anesthesiologist and collaborate with procedure team throughout the procedure
- Use cuffed tracheal tube
- Before RF ablation:
  - Announce the intent to start RF ablation
  - Reduce the oxygen concentration to the minimum required to avoid hypoxia, guided by patient monitoring
  - Stop the use of nitrous oxide
- Wait a few minutes before authorizing the use of RF ablation
- Refer to institutional requirements

The nodule/tumor will be accessed via EBUS bronchoscopy. If the nodule/tumor cannot be accessed via EBUS, or nodule/tumor is considered inappropriate for ablation by the treating physician, the subject will proceed to surgery and will not count against enrollment.

Under visualization with the EBUS bronchoscope, the ablation zone path length of the nodule/tumor will be measured using the EBUS measurement tool. If the path length is less than 1 cm, then a new ablation zone in the target nodule/tumor will be identified. The center of the ablation zone, should be at least 2 cm away from any critical structures, as determined by the investigator.

If an acceptable ablation zone cannot be determined, the subject will be considered a treatment failure. Tissue ablation parameters will be determined by the IFU.

The ANET applicator will be advanced to the target nodule/tumor under EBUS visualization. After the needle has been advanced into the target location, position may be confirmed using cone beam CT, intra-operative CT or fluoroscopy. The needle should be deep enough in the tissue and not extend past the distal margin of the target nodule/tumor. If it is not possible to place the needle appropriately, the subject will be considered a treatment failure.

Once the needle is placed correctly, a fixed electrode spacing of 1mm should be maintained for ablation. The target nodule/tumor can then be ablated per the energy application guidelines in the IFU. Saline flow post-RF delivery must be maintained to bring the tissue next to the electrode to baseline temperatures ( $\sim \geq 120$  s) and to arrest thermal damage to stated margins.

If the tumor is greater than 3.1 cm, than the energy parameters for no greater than a 3.1 cm ablation zone will be used.

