#### 9.1.6 Serious Adverse Event (SAE) (see Table 3.0 of Protocol Defined Serious

Adverse Events, below)

Adverse event that:

- a) led to a death,
- b) led to a serious deterioration in health that either:
  - 1) resulted in a life-threatening illness or injury, or
  - 2) resulted in a permanent impairment of a body structure or a body function, or
  - 3) required in-patient hospitalization or prolongation of existing hospitalization, or
  - 4) resulted in medical or surgical intervention to prevent life threatening illness or injury or permanent impairment to a body structure or a body function.
- c) led to fetal distress, fetal death or a congenital abnormality or birth defect.

NOTE 1: This includes device deficiencies that might have led to a serious adverse event if a) suitable action had not been taken or b) intervention had not been made or c) if circumstances had been less fortunate. These are handled under the SAE reporting system.

NOTE 2: A planned hospitalization for pre-existing condition, or a procedure required by the Clinical Investigation Plan, without a serious deterioration in health, is not considered to be a serious adverse event.

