**Table 2: Potential Adverse Events**

MedDRA term
Ablation site reactions

MedDRA term
(MedDRA term: Administration site reactions)
Abscess formation (MedDRA term: Wound Abscess)
Anaesthetic complication
Arrhythmia
Atelectasis
Bronchial obstruction
Bronchopulmonary hemorrhage
Bronchospasm
Burning or charring – unintended (MedDRA term: Burn local)
Cardiac arrest
Death
Device failure
Dyspnea
Electric shock
Esophageal hemorrhage
Hematoma (MedDRA term: Post-procedural hematoma)
Haemolysis
Haemoptysis
Hemorrhage
Hemothorax
Hypoxemia
Infection (acute)
Laryngeal spasm
Localized allergic reaction or irritant reaction (MedDRA term: Administration site hypersensitivity)
Microbubble/air embolism
Pleural effusion
Pleuritic pain
Pneumo-mediastinum
Pneumonia
Pneumonitis
Pneumothorax
Post-procedural hemorrhage
Postoperative thoracic procedure complication

MedDRA term
Pulmonary edema
Pulmonary embolism
Pulmonary fistula
Respiratory failure
Systemic toxicity
Soft tissue necrosis
Tumor recurrence (MedDRA term: Neoplasm recurrence)
Tumor seeding (MedDRA term: Treatment related secondary malignancy)

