### 9.1 Adverse Event (AE) Reporting by Investigator

Peri-procedural adverse events, defined as from the start of the EBUS bronchoscopy through the planned surgical resection, will be collected up to 30 days post procedure using the AE paper case report form. AEs shall be reported in accordance with study institution requirements, local vigilance systems, 21CFR 803 21CFR 812.46, 21CFR 812.140, and 21CFR 812.150, and ISO 14155:2011, sections 8.2.5 and 9.8.

Since this is a limited pilot study, there is no Data Safety Monitoring Board. In the event of an incidence of massive hemoptysis, acute respiratory distress, or a death that is device or ANET procedure related, as defined by the Principal Investigator, the study will be paused and the IRB and FDA will be notified.

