#### Onset of Multiple Adverse Events

If AEs occur concurrently, each event should be recorded on separate AE case report forms. However, if known at the time of reporting, a diagnosis should be recorded on the case report form rather than individual signs and symptoms (e.g., record congestive heart failure rather than dyspnea, rales and cyanosis). If a diagnosis is established from subsequent follow-up information post initial SAE reporting, the event term should be updated on the corresponding case report form to reflect the final diagnosis term.

If a constellation of signs and/or symptoms cannot be medically characterized as a single diagnosis or syndrome at the time of reporting, each individual adverse event should be recorded as a separate AE. Signs and symptoms that are considered unrelated to an encountered syndrome or disease should be recorded as individual AEs (e.g., if congestive heart failure and severe headache are observed at the same time, each event should be recorded as an individual AE on separate AE case report forms).

AEs occurring secondary to other events (e.g., sequelae) should be identified by the primary cause; a "primary" event, if clearly identifiable, and generally represents the most accurate clinical term to record as the AE event term.

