### 9.3 Unanticipated Serious Adverse Device Effect (USADE) Reporting by Sponsor

All SAEs that satisfy USADE criteria (see Section 9.1.7) will be reviewed by the study Medical Monitor, an independent physician consultant with subject matter expertise. The sponsor must report the results of an evaluation of an USADE to FDA and all reviewing IRBs and investigators within 10 working days after the sponsor first receives notice of the adverse device effect.

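### A survived, life-threatening, device-related event named in Table 2, such as cardiac arrest or air embolism, has no required pause and no required route to the independent Medical Monitor

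*Combined protocol and SAP*

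**What the plan says.** Section numbers 9.1 and 9.2 are each used twice in the protocol, so titles are given where needed.

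- **Oversight.** Adverse Event (AE) Reporting by Investigator (the second 9.1) states: "Since this is a limited pilot study, there is no Data Safety Monitoring Board".
- **Pause rule.** The same paragraph names the triggers: "massive hemoptysis, acute respiratory distress, or a death that is device or ANET procedure related, as defined by the Principal Investigator". The consequence is that "the study will be paused and the IRB and FDA will be notified". It does not say who reviews a pause or who permits restart.
- **Foreseen events.** Table 2 lists potential adverse events, including cardiac arrest, "Microbubble/air embolism", and death.
- **Seriousness.** Under section 9.1.6 an event is serious if it led to death (item a), or led to a serious deterioration in health that "resulted in a life-threatening illness or injury, or" met another of the listed consequences (the quoted words are item b)1)).
- **Anticipated or not.** Section 9.1.7 defines an unanticipated serious adverse device effect (USADE) by whether its nature, incidence, severity or outcome is already in the risk analysis report. A note there then treats everything in Table 2 as anticipated.
- **Independent review.** Section 9.3 states: "All SAEs that satisfy USADE criteria (see Section 9.1.7) will be reviewed by the study Medical Monitor". That person is described as an independent physician.
- **Other serious events.** Serious Adverse Event (SAE) Reporting by Investigator (the second 9.2) sends every serious event, anticipated or not, to the sponsor's site monitor within 2 working days of awareness.
- **Causality.** Event Causality uses a two-point scale: related if the timing fits, not related if clear evidence of a relationship is lacking.

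**The concern.** With no board, the pause rule and the Medical Monitor are the only written safeguards between one subject's serious device event and the next subject's treatment. Both leave out the same group of events: those the sponsor foresaw well enough to list, which turn out life-threatening but are survived. Listing an event in Table 2 makes it anticipated, and being anticipated removes it from independent review.

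At stake is whether another subject, possibly at another of up to 5 sites, can be treated after such an event under a protocol followed to the letter, with no independent physician having looked at it. Device-related safety is the primary endpoint. Section 8.2 offers subjects no direct benefit, and section 8.1 puts their safety first. The preclinical support is two swine studies of 6 animals each, which section 3 itself calls too few for meaningful statistical analysis.

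**Working it through.** The plan gives no figure to reproduce: section 12 states no hypothesis and calls the sample size of 10 arbitrary. The check follows one event through the text and then counts terms.

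**Following a survived, life-threatening, device-related air embolism**

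| Step | Provision | Result |
|---|---|---|
| 1 | 9.1.6 b)1) | Serious adverse event |
| 2 | 9.1.5 | Device-related, so a serious adverse device effect |
| 3 | Table 2 and the note in 9.1.7 | Listed, so anticipated |
| 4 | Table 3 | Anticipated serious adverse device effect, not a USADE |
| 5 | 9.3 | Not a USADE, so Medical Monitor review is not required |
| 6 | SAE reporting (9.2) | Reaches the sponsor's site monitor within 2 working days; no onward step stated |
| 7 | Pause rule (9.1) | Not one of the three triggers, so no required pause unless it also presents as one |

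A survived cardiac arrest follows the same path. Death differs only at step 7. A related death pauses the study, but death is also a Table 2 term, so steps 3 to 5 give it no stated route to the Medical Monitor either.

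**Counting Table 2 against the pause rule**

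- Terms in Table 2: 41.
- Direct match: 2 (death; haemoptysis, if massive).
- Arguable match through acute respiratory distress: 3 (dyspnea, hypoxemia, respiratory failure).
- No counterpart: 41 − 2 − 3 = 36, including cardiac arrest and air embolism.
- With a required route to the Medical Monitor under the 9.1.7 note: 0 of 41.

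**Looking for another safeguard**

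- Section 11.3.1 lists stopping rules as a topic for the initiation visit, but gives none.
- Section 11.2 item 1 covers sponsor reports of unanticipated effects only.
- Section 8.3.1 promises notice to sites of unexpected device effects and of other safety concerns, which it does not define. Notice is neither a pause nor an independent review.

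**Two internal conflicts on the same path**

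- In 9.1.7 the definition lets a known type of event count as unanticipated through its incidence, severity or outcome. The Table 2 note allows no such exception.
- The two causality definitions overlap. An event during ablation fits the timing test for related, and it may also lack clear evidence of a relationship, which fits not related.

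**Context only, on assumed rates.** The documents give no event rate. If the chance per subject of a serious event outside the triggers is p, the chance of at least one among 10 subjects is 1 − (1 − p)^10:

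- p = 2%: 18%
- p = 5%: 40%
- p = 10%: 65%
- p = 20%: 89%

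The finding does not depend on these figures.

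**The case against.** The strongest reply is that the text sets a minimum and forbids nothing. Every serious event reaches the sponsor within 2 working days, and the sponsor may pause or refer voluntarily. Section 8.3.1 could be read to require notice to other sites. Section 11 refers to a separate clinical study plan covering safety reporting, which is not among the documents. The study is small, and the absence of a board is disclosed with a reason. All of this stands. It limits the claim to what the protocol requires; it does not supply the missing requirement.

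A reader might infer more than the documents support:

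- **That such an event cannot pause the study or be reviewed.** The text only fails to require it. An arrest or embolism that presents as acute respiratory distress could meet a trigger.
- **That the investigator's causality opinion controls all three triggers.** The qualifier may cover all three or attach to death alone. Cardiac arrest and air embolism are unlisted on either reading.
- **That any event can easily be put down to the resection that follows.** An event during ablation meets the timing test for related. What the text shows is overlapping definitions.
- **That the triggers cannot arise under anesthesia, given the instruction "Use cuffed tracheal tube".** This is clinical inference, and events are collected to 30 days after the procedure.
- **That the recording rule, under which "a diagnosis should be recorded on the case report form rather than individual signs and symptoms", disables the triggers.** The pause depends on the event occurring, not on the term entered on the form.

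The 36 of 41 count also needs care. Table 2 includes terms such as pleuritic pain that nobody would expect to pause a study, so the count shows how narrow the rule is, not how many triggers are missing.

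**Conclusion.** The point holds as a gap in required escalation. Applied exactly as written, the protocol requires neither a pause nor independent medical review after a survived, life-threatening, device-related event that Table 2 names, unless it also presents as one of the three triggers. The gap in independent review is the wider of the two: under the 9.1.7 note it covers all 41 terms, including a death that does pause the study.

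This rests on two readings. The first is that the Table 2 note prevails over the broader definition beside it; if the definition prevailed, some listed events could reach the Medical Monitor through their incidence, severity or outcome. The second is that no further rule exists in these documents. A separate study plan might hold one, but a safeguard of this kind belongs in the protocol.

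**What to change.** 1. **Route to the Medical Monitor (SAE reporting 9.2, and 9.3).** Send every serious event meeting 9.1.6 a) or b)1), anticipated or not, to the existing independent Medical Monitor, who reviews both the event and the investigator's causality rating. Set the reporting time so that this review comes before further subjects are treated at any site; the present 2 working days does not ensure that.
2. **Pause rule (AE reporting 9.1).** Have the sponsor align the triggers with the protocol's own seriousness categories, state whether the relatedness qualifier covers all three events or death alone, and name who reviews a pause and who permits restart. Which events pause the study is for the sponsor and its clinical reviewers to decide.
3. **Reconcile the linked text.** Resolve the conflict between definition and note in 9.1.7 and its use of Table 2, remove the overlap in Event Causality, and make the stopping rules mentioned in 11.3.1 point to an actual rule.

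The cost is an amendment to several linked sections, a faster reporting step, and some added work for a Medical Monitor already in place. The downside is an occasional short hold for an event later judged surgical, in a study treating at most 10 subjects.

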#### Onset of Multiple Adverse Events

If AEs occur concurrently, each event should be recorded on separate AE case report forms. However, if known at the time of reporting, a diagnosis should be recorded on the case report form rather than individual signs and symptoms (e.g., record congestive heart failure rather than dyspnea, rales and cyanosis). If a diagnosis is established from subsequent follow-up information post initial SAE reporting, the event term should be updated on the corresponding case report form to reflect the final diagnosis term.

If a constellation of signs and/or symptoms cannot be medically characterized as a single diagnosis or syndrome at the time of reporting, each individual adverse event should be recorded as a separate AE. Signs and symptoms that are considered unrelated to an encountered syndrome or disease should be recorded as individual AEs (e.g., if congestive heart failure and severe headache are observed at the same time, each event should be recorded as an individual AE on separate AE case report forms).

AEs occurring secondary to other events (e.g., sequelae) should be identified by the primary cause; a "primary" event, if clearly identifiable, and generally represents the most accurate clinical term to record as the AE event term.

### Event Causality

All AEs will be assessed for relationship to the investigational device and/or the procedure on 2-point scale as follows:

**Related:** The AE has a timely relationship to the device or procedure.

**Not related:** There is no clear evidence that the AE has a relationship to the investigational device or procedure.

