#### 4.1.1 Primary Endpoints

Safety provided by the evaluation of peri-procedural device related adverse events produced by the ANET device used to ablate a target pulmonary nodule/tumor.

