### 8.3 Risks

- Risks of ANET ablation procedure and device are listed in Table 2, section 9.2 of this protocol.
- Patients will receive up to 3 additional CT's as a result of this study. These include a CT prior to and after ANET ablation. An additional CT may be taken to confirm needle location during the ANET ablation procedure.

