#### 9.1.2 Adverse Device Effect (ADE)

Adverse event related to the use of an investigational medical device.

NOTE 1- This includes any adverse event resulting from insufficiencies or inadequacies in the instructions for use, the deployment, the implantation, the installation, the operation, or any malfunction of the investigational medical device.

NOTE 2- This includes any event that is a result of a use error or intentional misuse.

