#### 9.1.7 Unanticipated Serious Adverse Device Effect (USADE)

Serious adverse device effect which by its nature, incidence, severity or outcome has not been identified in the current version of the risk analysis report.

NOTE: Anticipated: an effect which by its nature, incidence, severity or outcome has been previously identified in the risk analysis report. Adverse events listed in Table 2 below are considered anticipated for this study.

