**Table 3: Adverse Event Categories**

ADVERSE EVENTS	Non-device-related	Device- or procedure-related	
Non-serious	Adverse Event (AE)a (3.2)	Adverse Device Effect (ADE) (3.1)	
Serious	Serious Adverse Event (SAE)b (3.37)	Serious Adverse Device Effect (SADE) (3.36)	
		Anticipated	Unanticipated
		Anticipated Serious Adverse Device Effect (ASADE) (3.42, Note)	Unanticipated Serious Adverse Device Effect (USADE) (3.42)

a Includes all categories.
 
b Includes all categories that are serious.
			

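### The two causality categories overlap and pool device with procedure, so a Related entry does not identify the device-related AEs that form the primary endpoint

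*Combined protocol and SAP*

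**What the plan says.** The primary endpoint (Section 4.1.1 and synopsis) is "Safety provided by the evaluation of peri-procedural device related adverse events", with the ANET device named as the cause.

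The rating rule stands in Section 9.1, Adverse Event (AE) Reporting by Investigator, under Event Causality (the number 9.1 is also used for the definitions). It opens: "All AEs will be assessed for relationship to the investigational device and/or the procedure on 2-point scale". The two points are:

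- The Related category is worded as "The AE has a timely relationship to the device or procedure", which is a criterion of timing.
- The opposite category, Not related, is worded as "There is no clear evidence that the AE has a relationship to the investigational device or procedure", which is a criterion of evidence.

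Section 9.1.2 defines an adverse device effect as "Adverse event related to the use of an investigational medical device". Its notes bring in events arising from deployment, operation, malfunction, use error and misuse. Table 3 places ADE and SADE in a column headed "Device- or procedure-related".

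Section 5.2 has resection follow bronchoscopy and ablation at once. The reporting section sets the peri-procedural window from the start of EBUS bronchoscopy through the resection, with collection to 30 days. Section 12 plans summary results without a hypothesis. It says the sample of 10 is meant to give information on procedural and on device-related AEs, but gives no rule for deriving the device-related count.

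**The concern.** This is a first-in-human study without a comparator, and its primary result is a description of device-related AEs. Attribution by the investigator is therefore what turns a list of events into the primary result. If the rule allows two answers for the same event, investigators at up to 5 sites can each follow the protocol and still rate alike events differently. If the rule also merges the device with the procedure around it, even a consistent set of Related entries would not be the quantity that Section 4.1.1 names.

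**Working it through.** No arithmetic applies. The plan states no AE rate, precision target or success criterion, and Section 12 calls the sample of 10 arbitrary, so there is no figure to reproduce. The check is a comparison of the texts.

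**Step 1: are the two categories complementary?** Cross the two criteria that the rule uses.

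| Event | Meets Related (timing)? | Meets Not related (no clear evidence)? |
|---|---|---|
| Timely, clear evidence of a relationship | Yes | No |
| Timely, no clear evidence | Yes | Yes |
| Not timely, no clear evidence | No | Yes |
| Not timely, clear evidence | No | No |

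Read literally, the second row falls in both categories and the fourth in neither. The second row matters here: with ablation and resection back to back, an event close in time but of uncertain cause is an expected kind of event. A stricter reading of what counts as a relationship would shrink that row, but the text does not state one. The fourth row matters less, since an investigator with clear evidence would presumably choose Related.

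**Step 2: does Related yield the primary endpoint?**

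| Place | What it covers |
|---|---|
| Section 4.1.1 and synopsis | Device-related AEs, caused by ANET |
| Section 9.1.2 | AEs related to use of the device, including deployment, operation and use error |
| Event Causality, both categories | Device or procedure |
| Table 3, ADE/SADE column | Device or procedure |
| Section 12 | Procedural and device-related information, both named |

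The endpoint and the ADE definition are tied to the device. The rating rule and the Table 3 heading are not. An effect of the bronchoscopy unconnected with using the ANET device can be rated Related and sit in the ADE column, yet it is not an ADE under Section 9.1.2 and not part of the primary endpoint.

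**Step 3: can timing separate the sources?** Not from the rating alone. Bronchoscopy, ablation and resection follow one another inside a single window. The post-ablation bronchoscopic examination and CT (Section 7.2.3) help to place some events before surgery, but no analysis by onset is planned.

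**Step 4: what depends on the count?** Section 12 has no hypothesis. The study pause in the reporting section carries its own attribution wording, made by the Principal Investigator. The consequence is therefore limited to how the primary safety summary can be read.

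**The case against.** The case on the other side has several sound parts.

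- **The lead-in permits two ratings.** It speaks of device and/or procedure. The AE form, and the clinical study plan that Section 11 says will cover definitions and CRFs, are not in the documents. A reader might infer that no device-level rating exists; that cannot be shown. What stands is that the protocol text does not require one. Separate fields would not cure the overlap in Step 1.
- **Section 9.1.2 is not narrow.** A reader might take it as hardware only and set all of ablation against it. Its notes cover deployment, operation and use error, so ablation itself counts as use of the device. The gap between it and Table 3 is mainly EBUS and other procedural effects not tied to device use.
- **The intended procedure can be guessed.** Section 8.3 says "Risks of ANET ablation procedure and device are listed in Table 2, section 9.2 of this protocol", and the pause wording refers to the ANET procedure. This favours the ANET/EBUS procedure over the resection, but Event Causality does not say so, and that reading still mixes bronchoscopy effects with device effects.
- **Other safeguards exist.** AEs are monitored throughout, and data supporting the primary endpoint are fully source verified. Neither decides causality. A reader might go further and infer that listed events never reach the Medical Monitor, because "Adverse events listed in Table 2 below are considered anticipated for this study". That is one reading only: Section 9.1.7 also defines unanticipated by incidence, severity and outcome, and Table 2 lists terms without these, so an unusually severe listed event could arguably qualify.
- **With at most 10 treated subjects, events can be described case by case.** True, and it limits the harm. The case descriptions would still need a stated rule for which events belong to the primary endpoint.

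**Conclusion.** The point holds as a defect in a stated rule. Followed as written, the rule can classify the same event both ways, and a Related entry does not isolate the device-related AEs that Section 4.1.1 makes primary. The overlap follows from the wording alone and is certain on a literal reading. The pooling is less certain, because it assumes that the unseen AE form does not already ask for a separate device rating.

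Its size cannot be computed: the documents do not say how many events would be timely but of unclear cause. A reader might be tempted to express it as the shift in a proportion when one subject out of 10 is reclassified. That arithmetic is true of any reclassification in any study of this size, and the plan specifies no such proportion, so it does not measure this ambiguity. No test, power statement or success criterion is affected. It should be fixed because the repair is cheap and the count is the study's primary output.

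**What to change.** 1. Reword Event Causality so that the two categories are complementary on one stated criterion that combines timing and evidence, with Not related covering every event that does not meet it. The text should say where a timely event of uncertain cause goes.
2. Rate each AE separately for relationship to (a) use of the ANET device, including deployment, ablation, operation and use error as in Section 9.1.2, and (b) other procedures: EBUS bronchoscopy not tied to device use, anaesthesia and resection. State that rating (a) defines the primary endpoint, and report (b) separately. Ablation must stay under (a); otherwise true device effects could drop out of the primary count.
3. Align the Table 3 column heading with Section 9.1.2.

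If the AE form or clinical study plan already requires these separate ratings, it is enough for item 2 to say so in the AE reporting section and to name the rating that feeds the primary endpoint. A table of AEs by onset before or after the start of resection would be useful but is optional.

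The cost is a text change, possibly a revised AE form with slightly more entry per event, and re-rating of any AEs already recorded. No added subjects, visits or tests are needed.
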